NIHR Health Technology Assessment programme

National Institute for Health Research

NETSCC, HTA

23rd May 2011

PROTOCOL

Full Title: Faecal immunochemical testing (FIT) for adenoma surveillance

- Short Title: FIT for Follow-up study
- Sponsor: Imperial College London
- Principal Investigator: [name]

Co-investigators: [name] [name] [name] [name] [name] [name] [name]

Trial Steering Committee: [name] (chair) [name] [name] [name] [name] [name] [name] [name] [name] [name] [name] [name]

Contents

PROTOCOL	1
SUMMARY OF PROGRAMME	3
BACKGROUND	4
NEED FOR RESEARCH IN THIS AREA	4
AIMS AND OBJECTIVES	5
Primary aim	6
Secondary aims	6
RESEARCH PLAN	7
Eligible participants	7
Exclusion criteria: none	7
Sample Size	7
Planned Interventions	8
Identifying eligible people	8
Materials to be used in the study	9
FIT test	9
FIT testing/surveillance	9
FIT test processing	10
Patient experience questionnaires	10
ETHICAL CONSIDERATIONS	12
Risks and anticipated benefits for trial participants and society	12
Obtaining informed consent from participants	12
Proposed time period for retention of relevant clinical trial documentation	13
DATA ANALYSES	13
Primary outcome	13
Secondary outcomes	13
Economic analysis	14
SERVICE USERS	16
References	

SUMMARY OF PROGRAMME

The faecal immunochemical occult blood tests (FIT) are superior to the guaiac based faecal occult blood test (gFOBT) that is currently used in the NHS Bowel Cancer Screening Programme. They detect human globin in stool sample which avoids any dietary influence on positivity rates and newer versions are quantitative so that the threshold level for positivity can be varied. FITs are used in some bowel cancer screening programmes (Italy, Japan, Korea, Australia) to screen general population but in this study we propose to establish if they can be used as a safe, acceptable and cost-effective method of surveillance for people who are at increased risk of developing colorectal cancer because of a prior history of adenomas.

Our principal aim is to determine the 3-year programme sensitivity of annual faecal immunochemical test (FIT) for detection of advanced adenomas (AA) or colorectal cancer (CRC) in people who took part in the National Bowel Cancer Screening Programme and who were diagnosed with intermediate risk adenomas requiring colonoscopic surveillance.

Whilst waiting for their first surveillance colonoscopy, eligible participants will be asked to complete a FIT test once a year. Participants who are classified as being at intermediate risk of developing colorectal cancer will be asked to complete 3 annual FIT tests before undergoing their surveillance colonoscopy. If the result of the FIT test in year1 or year2 is positive their surveillance colonoscopy will be brought forward and they will not proceed to the next round of FIT testing.

Findings at surveillance colonoscopy will be used as gold standard against which we will measure the programme sensitivity and specificity of the FIT test.

Study participants, who consent to take part and complete a FIT test, will be asked to complete a questionnaire which will include general measures of quality of life and more specific instruments to monitor the psychological consequences of using the FIT.

BACKGROUND

Adenomas develop in a third of the population by age 60 [1]. Most are asymptomatic and are usually an incidental finding at colonoscopy, and most do not progress to malignancy [2]. Following adenoma removal, however, around 50% of people remain at increased risk of developing CRC or advanced adenomas (AA), which are those most likely to develop into cancer [3-5]. The risk of developing CRC and AA varies with the characteristics of previously removed adenomas [3-5]. Patients with large (\geq 1cm) or multiple adenomas removed are at intermediate or higher risk. Those with just 1-2 small adenomas are at low risk and averagerisk screening is probably adequate for them. The NHS Bowel Cancer Screening Programme (BCSP) uses a modification of the UK guideline for colonoscopy surveillance after adenoma removal [6] (Figure 1) which recommends colonoscopy surveillance only for the higher-risk groups. However, there are a number of problems in the use of colonoscopy for this purpose. It is not 100% sensitive and studies suggest that most AAs and CRCs detected at surveillance exams were already present but missed at the previous colonoscopy [4, 7]. In trials comparing different intervals between exams (from 1 to 4 years), more cancers have been detected in the longer-interval groups, suggesting that some missed AA progress to malignancy during this period [8]. Moreover, the detection rate of CRC or AA at each colonoscopy is only around 3%, so 97% of colonoscopies will either be negative or only detect small adenomas of low malignant potential [5, 9]. Colonoscopy is also a very expensive procedure, and in addition all colonoscopies carry a small risk of serious complications. Therefore the negative colonoscopies are costly and risky and provide no therapeutic benefit other than reassurance. Colonoscopy should therefore be reserved for cases where the benefits outweigh the risks and costs.

Surveillance following adenoma detection currently accounts for around one fifth of colonoscopies in the UK ([name], personal communication), but colonoscopy is also widely used to investigate colonic symptoms or a positive faecal occult blood screening test (FOBT) result. The use of FOBT in the Bowel Cancer Screening Programme has led to an increase in the number of colonoscopy referrals, to the point where the number of colonoscopies being undertaken is overwhelming the available endoscopy workforce. An alternative, more cost-effective method of protecting people with higher-risk adenomas is therefore urgently required.

NEED FOR RESEARCH IN THIS AREA

[figure not shown]
Most screening programmes use the guaiac-based faecal occult blood test (gFOBT), which has been shown to reduce CRC mortality rates in trials by up to 20% [10]. However, immunochemical faecal occult blood tests (FITs) incorporate several features that make them more suited for diagnosis of colorectal neoplasia in higher-risk groups. FITs use antibodies raised against the human globin component of haemoglobin and are not subject to interference from animal blood in the diet. They have higher sensitivity for CRC and AA than gFOBT [11-13], with higher positivity (recall) rates but similar positive predictive values. Some immunochemical tests can be automated and the cut-off level for positivity adjusted to change the sensitivity and specificity in different clinical settings. Several studies (involving a total of 108,804 people) have examined the performance of the FIT test in the screening context [12, 14-20]. The majority use the latex agglutination test (LAT) with a cut-off of 100ng haemoglobin/ml sample solution (as we propose) and achieve a positivity rate of 4%-6% using 1 or 2 samples per patient. The positive predictive value at first screen is around 10% for cancer and 20% for AA. Sensitivity for AA is around 25-30% but does not appear to decrease with repeated screening [21] and therefore programme sensitivity over 3 screenings should approach that of colonoscopy at 3 years. Therefore, annual FIT should detect most important lesions in people who would normally undergo 3-yearly colonoscopy surveillance and would result in fewer colonoscopies being undertaken overall.

Evidence on the use of immunochemical occult blood testing in higher-risk groups is limited to 3 studies [22-24]. In the first two studies (n = 252 and 169 respectively), patients with a familial risk of colorectal cancer used the FIT before colonoscopy, and sensitivities of 75% and 85% for AA were reported. In the third study, in which 611 patients with previously resected cancer used the FIT before colonoscopy, the FIT detected all 9 recurrent or metachronous cancers. There is no evidence on the programme sensitivity of FIT over more than one screening in higher-risk groups.

AIMS AND OBJECTIVES

The overall objective is to test the hypothesis that annual immunochemical faecal occult blood testing (iFOBT or FIT) is a feasible, safe, acceptable and cost-saving alternative to colonoscopy surveillance for the diagnosis of advanced adenomas (AA) and early stage colorectal cancer (CRC) in patients with intermediate risk colorectal adenomas as defined by national guidelines (see Figure 1).

Figure 1: Surveillance Guidelines

SURVEILLANCE FOLLOWING ADENOMA REMOVAL

Primary aim

• To determine the 3-year programme sensitivity of annual FIT for detection of AAs or CRCs compared with colonoscopy undertaken at 3 years in patients with intermediaterisk adenomas detected following a positive faecal occult blood test (gFOBT) completed as part of the Bowel Cancer Screening Programme (BCSP) in England.

Secondary aims

- To examine the acceptability of FIT compared with colonoscopy as an alternative method of surveillance for people at an increased risk of CRC.
- To calculate the incremental costs and cost-effectiveness of FIT vs. colonoscopy surveillance.
- To model the potential of FIT screening to replace colonoscopic surveillance for groups at intermediate risk of developing CRC such as those with a personal or family history of CRC but not a dominantly-inherited syndrome. These groups pose a major resource problem for endoscopy units.

RESEARCH PLAN

This is a pragmatic accuracy and efficiency study to assess programme sensitivity of annual FIT using colonoscopy at 3 years in those testing negative as a reference standard. The study will also address acceptability and cost-effectiveness of annual FIT as an alternative to 3-yearly colonoscopy for adenoma surveillance.

Eligible participants

Table 1 shows the range of possible case yield and sample size assuming 40% attrition. By definition, we are taking our study population from those who have complied with initial referral to colonoscopy. It is therefore likely that our population is more motivated than the population in general, and our anticipated rates of further participation are therefore likely to be conservative. If we assume that 65% of those recruited comply with the first FIT, that we lose a further 20% of those remaining at either the second or third FIT episodes, and that 80% of those remaining fully compliant attend their surveillance colonoscopy, we are left with a proportion fully compliant of 0.4 (0.65 x 0.8 x 0.8). With the most conservative assumptions on relative programme sensitivity (75%) and AA/CRC prevalence (2.5%), and allowing for a compliance rate of 40% requires a maximum sample size of 8000 (see Table 1).

Planned Interventions

Identifying eligible people

People with intermediate risk adenomas will be identified in the Bowel Cancer Screening Programme database by the Connecting for Health team in Exeter who will send us a dataset with participants' contact details. This dataset will be stored securely on servers in a data centre provided by IOKO. This company provides a secure managed hosting facility compliant with all the current regulatory requirements governing the NHS data storage and they work with around 200 NHS organisations at present. Secure access to the data centre would be provided from a few identifiable computers over a virtual private network connection (VPN). Data exchange would be encrypted and access controlled by the use of strong passwords. IOKO will provide a fully managed service, in line with industry standards including daily monitoring and backups. The details of all the eligible people will initially be available only to the NHS staff at South of England Bowel Cancer Screening Programme Hub. Once people consent to take part in the study, their details will become available to the research team at the Imperial College.

Materials to be used in the study

Please, see Appendix 1

FIT test

We will use the semi-quantitative immunochemical faecal occult blood test OC-SENSOR produced by Eiken Chemical Co., Tokyo, Japan and distributed by MAST group Ltd., UK. The FIT kit contains written instructions and a single sampling tube, with 2 ml haemoglobin stabilising buffer. The users are asked to collect the sample on a single occasion and to post it immediately to the processing laboratory (Bowel Cancer Screening Programme – South of England Hub, Postgraduate Medical School, University of Surrey, [name])

FIT testing/surveillance

Round 1 (Yr 1): All the eligible people will be sent a FLYER to alert them to our study around 1 year after the colonoscopy at which intermediate risk adenomas were detected. A week later, an INVITATION to take part in the study will be sent, together with detailed patient information sheet, a consent form and a FIT kit.

Those who do not respond to this invitation within 3 weeks will be sent a REMINDER and a replacement kit if required.

People who give their consent and return a completed test will form our sample and will be required to complete 2 further rounds of FIT testing.

Those who test positive at the first FIT will be offered immediate colonoscopy in the Bowel Cancer Screening centre that is responsible for their surveillance and will return to point B in the BSG guideline algorithm (Figure 1). They will not receive FIT kits in years 2 and 3.

Round 2 (Yr 2): Patients who test negative in the first round will be sent another FIT one year later. Those who test positive at the second round will be offered immediate colonoscopy and will return to point B in colonoscopic surveillance programme (Figure 1).

Round 3 (Yr 3): People who test negative at years 1 and 2 together with those who did not complete their test in Round 2 will be sent another FIT at 3 years. These people will all be invited for the routine surveillance colonoscopy due at 3 years, irrespective of the FIT result,

and will return to point B in colonoscopic surveillance programme as depicted in Figure 1. All lesions detected at colonoscopy would be removed and subjected to pathological assessment, as is the usual practice. Both patients and their GPs will be informed of the results of each completed FIT test in each round.

FIT test processing

People who take part in the study will mail their used kit in prepaid, addressed envelopes to the laboratory of the Bowel Cancer Screening Programme South of England Hub. The kits will be processed as per the manufacturer's instructions and the results from the processor will be uploaded into the database. The positivity threshold will be set at 100 ng haemoglobin/ml sample solution as was used in other studies (14-20).

A proportion of tests will be spoilt either due to inappropriate handling by users or due to technical faults in the laboratory. In such cases participants will be offered a chance to repeat the test and a new kit would be sent to them.

[figure not shown]
Patient experience questionnaires

[figure not shown]
Throughout the study, we will assess various aspects of patient experience including the acceptability and psychological consequences of annual surveillance using a home-based faecal immunochemical testing.

In order to study the emotional consequences of FIT surveillance we will assess general mood before completing the first Fit test and then after each round of FIT surveillance. Our itinerary of questions to monitor emotional impact include the short version of the Spielberger State Anxiety Inventory (STAI) (27) and more specific measures of bowel-cancer related worry which has previously been used to study the psychological impact of being offered colonoscopic surveillance [26]. We also use three items from the emotional subscale of the positive psychological consequences of screening questionnaire to ascertain the degree of reassurance gained after each round of FIT surveillance (28).

In Rounds 1 and 2 questionnaires will be administered with the receipt of final testing outcomes (i.e. a negative FIT result letter or letter informing participants of the outcomes of their diagnostic colonoscopy). In order to avoid unnecessary distress we shall not mail questionnaires to those with a diagnosis of cancer. In the final round of FIT surveillance, questionnaires will be administered with the letter informing patients about the outcome of their 3-year surveillance colonoscopy.

Flow of the participants through the study and planned interventions are shown in Figure 2 below.

ETHICAL CONSIDERATIONS

Risks and anticipated benefits for trial participants and society

The anticipated benefits for society and for future patients found to have intermediate risk adenomas include avoidance of the need for regular colonoscopic surveillance, which carries a measurable risk of serious complications. In addition the alternative method of surveillance we have proposed – stool testing with a sensitive FIT - would be more convenient as it can be conducted at home, with the inconvenience of colonoscopy restricted to those who test positive (expected to be less than 20% over 3 years). There are additional anticipated benefits to society such as cost-saving and better use of endoscopy resources by replacing some of colonoscopic surveillance with FIT.

Inviting people who have had colonoscopy and have been told they need a colonoscopy in three years' time may heighten their perception of their risk of colorectal cancer and possibly increase doubts about the effectiveness of colonoscopy in preventing colorectal cancer. During the study, they will have additional protection against development of cancer as they will undergo FIT testing annually *in addition* to their 3-year surveillance colonoscopy. However, patients need to understand that around 1 in 10 people participating in the study will require an early colonoscopy because they will have a positive FIT at Years 1 or 2. Around one half of people having an early colonoscopy will have no adenomas detected, so the early colonoscopy will not be of benefit to them. Conversely, some people will have advanced adenomas detected and for these people it will be an advantage to have important lesions found and treated earlier.

There are no additional risks since there will not be an increase in the number of recommended colonoscopies Participants, who have an early colonoscopy because of a positive FIT test at years 1 or 2, will have their next scheduled colonoscopy 3 years later. The current guideline for adenoma surveillance recommends that patients with intermediate adenomas should have two negative exams before stopping surveillance.

Obtaining informed consent from participants

We have engaged service users with the project in order to get their input in drafting clear and understandable information for participants to ensure that they are able to give fully informed consent. Their suggestions have been incorporated in the materials we submit with this application (see Appendix1). The consent form and comprehensive patient information sheet will be posted to potential participants and they will be encouraged to discuss the materials with members of their families, friends and GPs. A proportion of people may want to discuss

the study and potential implications of their taking part with a member of staff so we provided a help-line number and a half-day training course for staff manning the help-line.

Proposed time period for retention of relevant clinical trial documentation

The Imperial College Clinical Research Governance Office requires that all primary research data be retained for a minimum period of 10 years following completion of the study. We shall endeavour to ensure that the study is conducted ethically and efficiently. We shall establish a Trial Steering Committee (TSC) which will meet bi-annually. Imperial College research governance procedures will ensure that all appropriate regulations and guidelines are followed.

DATA ANALYSES

Primary outcome

 The cumulative yield of CRC/AA in those testing positive on any one of the three annual FITs, relative to the total CRC/AA (those testing positive on any of the FITs plus additional CRC/AA cases detected at the 3-year colonoscopy in those testing negative at all three FITs). From this, we can calculate the proportion of cases which would go undetected if the FIT regimen was standard.

Secondary outcomes

- Completion and positivity rates for 1st, 2nd and 3rd annual FITs.
- Positive predictive values for the detection of CRC/AA at the 1st, 2nd and 3rd FIT screenings in patients who undergo colonoscopic investigation.
- Detection rate of CRC/AA at the 3-year colonoscopy in patients who test negative at the 1st, 2nd and 3rd FIT screening.
- Subjective physical and mental well-being following 1st, 2nd and 3rd annual FITs (e.g. the impact positive vs. negative FIT screenings, interval colonoscopies etc.)
- Preference for annual FIT vs. 3-yearly colonoscopy for surveillance and satisfaction with FIT at the 3 year assessment.
- Incremental costs and cost-effectiveness of the FIT regimen versus three-year colonoscopy surveillance.

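### The 3-year preference and satisfaction outcome has no delivery route to participants FIT-positive at year 1 or 2, or to those who miss the 3-year colonoscopy

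*Protocol*

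**What the plan says.** The Protocol's list of secondary outcomes (Data Analyses) includes "Preference for annual FIT vs. 3-yearly colonoscopy for surveillance and satisfaction with FIT at the 3 year assessment". The well-being outcome just above it is timed differently, after each of the three annual FITs.

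The section Patient experience questionnaires begins: "Throughout the study, we will assess various aspects of patient experience including the acceptability and psychological consequences". It names a short anxiety inventory, bowel-cancer worry measures and three reassurance items. It then fixes delivery:

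- "In Rounds 1 and 2 questionnaires will be administered with the receipt of final testing outcomes". For FIT-positives this is the "letter informing participants of the outcomes of their diagnostic colonoscopy".
- In the final round, "questionnaires will be administered with the letter informing patients about the outcome of their 3-year surveillance colonoscopy".
- One group is left out by rule: "we shall not mail questionnaires to those with a diagnosis of cancer".

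Under FIT testing/surveillance, Round 3 and the routine 3-year colonoscopy are for people negative in both earlier rounds and those who missed the Round 2 test. Under Risks and anticipated benefits, the Protocol expects that "around 1 in 10 people participating in the study will require an early colonoscopy" after a positive FIT at year 1 or 2, and says that these participants "will have their next scheduled colonoscopy 3 years later".

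**The concern.** The outcome is tied to year 3, and the only final-round trigger is a letter that some participants will never be sent. Whether someone is asked at 3 years therefore depends on their own FIT results and on whether they accepted the 3-year colonoscopy. Both could plausibly be related to how they view FIT and colonoscopy.

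Acceptability of FIT compared with colonoscopy is the first secondary aim, and acceptability is part of the overall hypothesis. A colonoscopy brought forward by a positive FIT is a burden specific to the FIT regimen, and the Protocol expects about half of these examinations to find no adenoma. If nobody with that experience answers at 3 years, their 3-year preference cannot be estimated. This is a data-collection rule, so no later choice of analysis can supply the missing answers.

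**Working it through.** **1. Who receives which form, under the stated triggers**

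| Group | Round 1/2 form | Final-round form |
|---|---|---|
| FIT-positive at year 1 or 2, no cancer | Yes, with diagnostic colonoscopy outcome | No trigger: no 3-year surveillance colonoscopy |
| FIT-positive at year 1 or 2, cancer | No, by rule | No |
| Not positive in years 1 and 2, attends 3-year colonoscopy (any year-3 FIT result) | Yes, with negative FIT results | Yes, unless cancer |
| Not positive in years 1 and 2, does not attend | Yes, with negative FIT results | No trigger: no outcome letter |

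An early colonoscopy at about year 1 or 2, with the next one 3 years later, puts that next one at about year 4 or 5. Round 3 FIT-positives are covered, but everyone in Round 3 is invited to colonoscopy whatever the FIT shows, so theirs was due anyway.

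**2. Share of early positives**

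Input: positivity p of 4% to 6% per round (Need for research in this area). Assumptions: rounds independent, full uptake. Share positive by year 2 = 1 − (1 − p)².

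- p = 4%: 1 − 0.96² = 7.8%
- p = 5%: 1 − 0.95² = 9.8%
- p = 6%: 1 − 0.94² = 11.6%

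This reproduces the Protocol's figure of about 1 in 10. Over three rounds, 1 − (1 − p)³ gives 11.5% to 16.9%, consistent with its expectation of less than 20%.

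**3. Number of people**

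Inputs from Sample Size: maximum sample 8000, 65% completing the first FIT. 8000 × 0.65 = 5200. At 10%, 520 people are early positives (5200 × 0.0784 = 408 to 5200 × 0.1164 = 605). If all have the early colonoscopy and half have no adenoma, that is about 260.

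**4. Effect of omitting early positives on overall preference**

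Let w be the share omitted, and let p_R and p_E be the proportions preferring FIT among the rest and among early positives. Reported minus true = w × (p_R − p_E). The Protocol gives no value for the difference, so these are assumptions, at w = 0.10:

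| Assumed difference (points) | Shift (points) |
|---|---|
| 10 | 1 |
| 20 | 2 |
| 40 | 4 |
| 60 | 6 |
| 100 (limit) | 10 |

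At the limit, the shift is 7.8 to 11.6 points over the positivity range. If early positives prefer FIT more than the others do, the sign reverses.

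**5. Non-attenders**

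Sample Size assumes that 80% of those still fully compliant attend the surveillance colonoscopy. Applying that rate to everyone not early positive (an assumption) gives 0.90 × 0.20 = 0.18 of participants without a letter. They add a second term, 0.18 × (preference among attenders − preference among non-attenders), also of unknown sign.

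**The case against.** A reader might infer that early positives are never asked anything, or that acceptability as a whole is estimated without the people who bore the burden of a positive FIT. The Protocol does not support that. Early positives without cancer are sent a questionnaire with the outcome of their diagnostic colonoscopy, acceptability is to be assessed throughout the study, and the well-being outcome expressly compares positive with negative FITs and covers interval colonoscopies. Completion rates for each FIT do not depend on the final mailing.

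The item content of each form is not described in the text. The materials are in an appendix and the flow is in a figure, neither of which is available here, so the Round 1/2 form may already carry preference or satisfaction items. Coverage of early positives cannot be put at zero. It is also arguable that the 3-year timing attaches only to satisfaction, and the Protocol does not define the 3-year assessment as the form sent with the colonoscopy letter.

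A reader might also infer that preference for FIT will be inflated. That is not established. The Protocol notes that some early positives gain from having important lesions found sooner, and they may favour FIT. The 80% attendance is a planning figure, with participation rates described as likely conservative, and no decision rule rests on preference.

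These points limit the finding but do not remove it. The text names no other final-round mailing, and answers given in Round 1 or 2 would not supply an outcome set at 3 years. On the alternative reading, satisfaction would still be affected and preference would have no stated time.

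**Conclusion.** The point holds for the 3-year preference and satisfaction outcome only. As written, that outcome has no delivery route to participants FIT-positive at year 1 or 2, or to non-attenders at the 3-year colonoscopy, and no 3-year respondent will have had a colonoscopy brought forward by a FIT.

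The early positives are about 10% of participants (7.8% to 11.6%, with independent rounds and full uptake). The shift in overall preference from leaving them out has unknown sign, is 1 point for each 10 points of difference between the groups, and cannot exceed about 8 to 12 points. Non-attendance adds a further unsigned component. The overall shift is likely to be modest; the larger loss is that 3-year preference in the early positives cannot be described at all. The conclusion assumes that the materials not shown contain no separate 3-year mailing. Other acceptability measures and the primary outcome are unaffected.

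**What to change.** Either of two changes would do.

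1. Mail the 3-year preference and satisfaction form by calendar date to all participants, whatever their earlier FIT result or colonoscopy attendance, keeping the cancer exception. Setting the date after the 3-year colonoscopies are normally complete keeps attenders' answers after the examination. Cost: one extra mailing to about 10% of participants plus non-attenders (about 18% more on the planning attendance).
2. Put the same items on the Round 1/2 questionnaire for FIT-positives, or state that they are already there, and amend the outcome's timing to match. Cost: a few items on a form already sent. Early positives would then answer at a different time from everyone else, and 3-year non-attenders would still be missed.

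With either option, report preference and satisfaction overall and separately for early positives. If neither is adopted, the outcome's population should at least be defined as those who reach the 3-year colonoscopy letter. That makes the result honest but leaves the selection in place.
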